	
 
restrictions of use.
 
To assess duration of use and cumulative dose of nomegestroland chlormadinone- containing products before and after the implementation of restrictions of use.
 
To describe characteristics of users of relevant drug classes before and after implementation of the restrictions of use.
 
To describe the line of treatment in users of nomegestrol- and chlormadinone- containing products before and after the implementation of the restrictions of use for high dosed products.
 
	
	

To describe the frequency of patients who develop meningioma during treatment with products containing NOMAC or CMA, and

	

Authors: [name], [name], [name], [name], [name] Version: V4.0

Dissemination level: Public

	
 
those who discontinue or switch to alternative treatments before and after implementation of the restrictions of use.
 
6. To assess the impact of the restrictions of use adopted in 2018 and 2022 in incident prescriptions of nomegestrol- and chlormadinone-containing products.
 

Countries of study	Belgium, Croatia, Germany
Authors	[name] ( [contact] ) [name] ( [contact] ) [name] ( [contact] ) [name] ( [contact] ) [name] ( [contact] )

Authors: [name], [name], [name], [name], [name] Version: V4.0

Dissemination level: Public

## **LIST OF ABBREVIATIONS**

Acronyms/terms	Description	
ARIMA	Autoregressive Integrated Moving Average	
ATC	Anatomical Therapeutic Chemical	
CDM	Common Data Model	
CI	Confidence Interval	
CIPH	Croatian Institute of Public Health	
CMA	Chlormadinone acetate	
COVID-19	Coronavirus disease 2019	
CMHP	Committee for Medicinal Products for Human Use	
DARWIN EU®	Data Analysis and Real-World Interrogation Network	
DHPC	Direct Healthcare Professional Communication	
EHR	Electronic Health Record	
EMA	European Medicines Agency	
EU	European Union	
FinOMOP	Finnish Care Register for Health Care	
GDPR	General Data Protection Regulation	
GP General Practitioner		
HR	Hazard Ratio	
HRT	Hormonal Replacement Therapy	
IQVIA DA	IQVIA Disease Analyzer	
IQVIA LPD IQVIA Longitudinal Patient Database		
ITS Interrupted Time Series		
MAH	Marketing Authorisation Holders	
NAJS	Croatian National Public Health Information System	
NOMAC	Nomegestrol acetate	
OHDSI	Observational Health Data Sciences and Informatics	
OMOP Observational Medical Outcomes Partnership		
PRAC	Pharmacovigilance Risk Assessment Committee	
RR	Risk Ratios	
RMM	Risk Minimisation Measures	
SMD	Standardised Mean Differences	
SNOMED	Systematised Nomenclature of Medicine	
WHO	World Health Organisation	

P3-C3-006 Study Protocol	
Authors: [name], [name], [name], [name], [name]	Version: V4.0
[name], [name]	Dissemination level: Public

## 1. TITLE

DARWIN EU® - Impact of risk minimisation measures related to the risk of meningioma in women using nomegestrol and chlormadinone

## 3. ABSTRACT

#### **Title**

DARWIN EU® – Impact of risk minimisation measures related to the risk of meningioma in women using nomegestrol and chlormadinone

#### Rationale and background

Nomegestrol acetate (NOMAC) and chlormadinone acetate (CMA) are synthetic progestins indicated for the treatment of several gynaecological and menstrual disorders, as hormone replacement therapy and as hormonal contraception. Recent epidemiological studies have found a dose-dependent association between NOMAC or CMA and meningioma. As a result, risk minimisation measures (RMM) were implemented in 2022, especially for high-dose products, which should be used at the lowest effective dose and for the shortest duration possible and should not be used for first-line treatment. For all products containing NOMAC or CMA, treatment was contraindicated in patients with meningioma or a history of meningioma. All patients should be monitored for symptoms of meningioma and treatment should be permanently discontinued if diagnosed with meningioma during treatment. This contraindication was already in place for NOMAC, with previous regulatory actions implemented in 2018 and 2020.

#### Research question and objectives

The overall aim of the study is to describe how prescribing of NOMAC and CMA containing medicines (as single active ingredients and combinations with oestrogen) has changed following the EU-wide introduction of RMM in November 2022. To contextualise findings, changes in other relevant drug classes will also be described. This will include progestogen and oestrogen combination products and progestogens that are pregnadien derivates (see "Variables").

[figure not shown]
The specific objectives are:

- 1. To assess the monthly prevalence and incidence of use of drug classes of interest before and after the implementation of the restrictions of use.
- 2. To assess duration of use and cumulative dose of products containing NOMAC or CMA before and after the implementation of restrictions of use.
- 3. To describe characteristics of users of relevant drug classes before and after implementation of the restrictions of use.
- 4. To describe the line of treatment (2nd/3rd versus 1st) in users of products containing NOMAC or CMA before and after the implementation of the restrictions of use.
- 5. To describe the frequency of patients who develop meningioma during treatment with products containing NOMAC or CMA, and those who discontinue or switch to alternative treatments before and after implementation of the restrictions of use.
- 6. To assess the impact of the restrictions of use adopted in 2018 and 2022 in incident prescriptions of products containing NOMAC or CMA.

#### Methods

#### Study design

Retrospective cohort studies will be conducted using routinely collected health data from 3 databases from 3 countries in Europe. The study will comprise of:

- 1. A population-level drug utilisation study (DUS) to assess incidence/prevalence of drug classes of interest (objective 1).
- 2. A patient-level DUS to describe:
  - a. Treatment duration and cumulative dose over a specific time window spanning 6 or 12 months, depending on data availability (objective 2)
  - b. Characteristics of new users (objective 3)
  - c. Line of treatment (objective 4)
  - d. Switching to alternative treatments (objective 5)
- 3. A trend analyses and effectiveness of risk minimisation measures to assess changes in:
  - a. Patient-level analyses (objective 2 to 5)
  - b. Population-level analyses (objective 6, based on results of objective 1)

#### Population

The source population will comprise all females aged >10 present in the database at any time during the period from  $1^{st}$  of January 2010 (or start according to the database) to end of data availability. All patients need to have at least 365 days of data visibility prior to index date.

For patient-level DUS, the study population will be additionally restricted to new medicine users:

- Objective 2, 4 and 5: Participants newly prescribed with NOMAC or CMA.
- Objective 3: Participants newly prescribed with any drug classes of interest.

### **Variables**

#### Drug classes of interest:

- Progestogen and oestrogen combination products (WHO ATC G03AA, G03AB, G03FA and G03FB)
- Progestogens that are pregnadien derivates (WHO ATC G03DB)

#### Progestogens of interest:

- Medroxyprogesterone (WHO ATC G03AC06, G03DA02, G03AA17, G03FA12, G03FB06, G03AA08)
- NOMAC (WHO ATC G03AA14, G03DB04, G03FB12)
- CMA (WHO ATC G03AA15, G03AB07, G03DB06, G03FB03)

#### **Exposures**

- Objective 1: N/A
- Objective 2, 4 and 5: First-ever prescription of NOMAC or CMA (assessed separately)
- Objective 3: First-ever prescription of NOMAC or CMA (assessed separately)
- Objective 6: N/A

#### **Outcomes**

- Objective 1: Prescribing of drug classes or progestogens of interest (assessed separately)
- Objective 2: N/A (treatment duration and cumulative use of exposures)
- Objective 3: N/A (characterisation)
- Objective 4: Prescribing of alternative drug classes of interest not containing NOMAC or CMA
- Objective 5: Number of meningioma cases during treatment. Discontinuations or switches to alternative drug classes of interest not containing NOMAC or CMA.
- Objective 6: Prescribing of NOMAC or CMA.

Authors: [name], [name], [name], [name], [name]

Version: V4.0

Dissemination level: Public

#### Timing of the intervention

- Main intervention of interest: November 2022 to January 2023.
- Additional intervention related to NOMAC (Objective 6 only): October 2018 to January 2019.

## Covariates for stratification:

- Age group: 10-17, 18-34, 35-49, 50-64, +65 years (Objective 1)
- Dose: High- vs. low- dose, for NOMAC and CMA only (Objective 1,4,6)
- Indication: HRT (hormonal replacement therapy) vs. non-HRT, with age as a proxy (Objective 1,2,4,6)
- WHO ATC 5th level code: For NOMAC and CMA only (Objective 1 and 5).
- Study period: Pre- vs. Postintervention (Objective 1 to 5).

#### Data sources

- 1. IQVIA Disease Analyzer Germany (IQVIA DA Germany)
- 2. IQVIA Longitudinal Patient Database Belgium (IQVIA LPD Belgium)
- 3. Croatian National Public Health Information System (NAJS), Croatia

#### Sample size

No specific sample size calculations have been performed. The expected number of patients exposed to NOMAC or CMA is expected to be roughly between 1,900 in NAJS and 16,800 in IQVIA DA Germany and between 2,4004 in IQVIA LPD Belgium and 173,900 in IQVIA DA Germany, respectively, for the entire source data.

#### Statistical analyses

#### Objective 1:

We will calculate incidence rates and period prevalence of drug classes and progestogens of interest (assessed separately). Results will be reported overall and stratified by study period, age group, dose, indication (HRT vs. non-HRT) and WHO 5th ATC level codes (if counts allow).

#### Objective 2:

Treatment duration will be reported for the first prescribed treatment. Cumulative dose will be calculated considering all treatments containing NOMAC or CMA recorded during the study period. For the pre- and postintervention comparison, cumulative dose and treatment will be calculated for all treatments initiated over one year before (or six months, if insufficient follow-up data is available) and after the intervention.

Exposures of interest (NOMAC vs. CMA) will be assessed separately. Results will be reported overall and stratified by study period and indication at first use.

#### Objective 3:

Characteristics will be described by means of large-scale characterisation. Pre-specified comorbidities and concomitant medications will also be described. Covariates will be reported as counts and proportions. Results will be reported overall and stratified by study period.

#### Objective 4:

Line of treatment will be retrospectively assessed by looking at the occurrence of records indicating the use of other drug classes of interest not containing NOMAC or CMA from the day before index date to the start

D2	C2	OOC	Chinds	. Dund	
P3:	·L3·	บบธ	Study	v Proi	.OCOI

Version: V4.0

**Dissemination level: Public** 

of the study period. Line of treatment will be reported as first vs. non-first treatments. Exposures of interest (NOMAC vs. CMA) will be assessed separately. Results will be reported overall and stratified by study period, dose at index date and indication at index date.

#### Objective 5:

We will describe the frequency of switches of treatment with NOMAC or CMA to products of other relevant drug classes not containing NOMAC or CMA within 180 days after the end of treatment. We will also describe the number of patients discontinuing treatment. The number of meningioma cases occurring any time during treatment with NOMAC or CMA, and in the six months prior to treatment discontinuation will also be reported. Exposures of interest (NOMAC vs. CMA) will be assessed separately.

Results will be reported overall and stratified by study period and WHO 5th ATC level codes (if counts allow).

#### Objective 2 to 5:

Standardised mean differences of each of the covariates for the comparison of drug users in the pre-RMM and post-RMM period as a measure of the impact of the profile of drug users. These covariates will include: duration and cumulative dose (objective 2), patient characteristics in terms of prior comorbidities (objective 3) and line of treatment (objective 4). For objective 5, these will include the proportion of patients discontinuing orswitching treatments (assessed separately), and the proportion of patients diagnosed with meningioma during treatment.

#### Objective 6:

The impact of the restrictions of use will be estimated using an interrupted time series analysis (segmented regression) and will be informed by results obtained as part of objective 1, only if trends can be transformed to be linear and if no residual autocorrelation is detected. For NOMAC, the intervention adopted in October 2018 will also be assessed. Results will be reported overall and stratified by dose and indication.

#### 4. AMENDMENTS AND UPDATES

None.

## 5. MILESTONES

Study milestones and deliverables	Planned dates
Draft Study Protocol	November 2024
Final Study Protocol	January 2025
Creation of Analytical code	February 2025
Execution of Analytical Code on the data	March/April 2025
Draft Study Report	May 2025
Final Study Report	May 2025

P3-C3-006 Study	v Protocol
-----------------	------------

Version: V4.0

Dissemination level: Public

#### 6. RATIONALE AND BACKGROUND

Medicines containing nomegestrol acetate (NOMAC) or chlormadinone acetate (CMA) are synthetic progestins with antiandrogenic effects. Approved indications for NOMAC and CMA in monotherapy or in combination with oestrogens differ between different strengths and different countries. In general, they are indicated for gynaecological and menstrual disorders, hormone replacement therapy (HRT) and, at lower doses, as hormonal contraception.

Meningioma is a rare tumour that forms from the meninges. Known risk factors for meningioma are being female, exposure to ionising radiation and neurofibromatosis type 2.(1) Recently published studies have found a dose-dependent association between NOMAC or CMA and meningioma.(2-5) The hazard ratio (HR) of intracranial meningioma adjusted for age was 4.5 (3.5-5.7) and 4.4 (95% CI 3.4-5.8) among women exposed to NOMAC and CMA, respectively.(2, 3) The risk of meningioma increased with dose and duration of treatment and diminished one year after the discontinuation of treatment. Prolonged exposure to progestogens other than NOMAC such as cyproterone acetate (6) and medroxyprogesterone acetate (7) has also been linked to an increased risk of meningioma.

The risk of meningioma associated with NOMAC is known since 2018 and has been assessed within different regulatory procedures.(8) In October 2018, the Pharmacovigilance Risk Assessment Committee (PRAC) recommended to amend the product information of monotherapy products containing NOMAC to include the contraindication for patients who have, or have had, meningioma. PRAC also recommended permanently discontinuing treatment in patients who develop meningioma. In 2020, the product information of products containing NOMAC in combination with oestradiol was updated with similar contraindications and warnings.

In July 2022, PRAC issued further recommendations for both NOMAC and CMA. PRAC recommended to update the summary of product characteristics for products containing NOMAC or CMA to inform of the risk of meningioma. PRAC recommended that medicines containing high-dose chlormadinone (5 – 10 mg) or high-dose NOMAC (3.75 – 5 mg) should be used at the lowest effective dose and for the shortest duration possible. These medications should only be used when other interventions are not appropriate and should no longer be considered for first-line treatment. Similar to what was already established for NOMAC, treatment with products containing NOMAC or CMA was contraindicated in patients with current or prior history of meningioma. PRAC also recommended monitoring patients for symptoms, and permanently discontinuing treatment if the patients develop meningioma. (9) Measures recommended by PRAC were endorsed by the Committee for Medicinal Products for Human Use (CHMP) and the European Commission issued final legally binding decisions applicable in all the European Union (EU) Member States, between 28th of October and 28th November 2022.(10) Following this decision, a direct healthcare professional communication (DHPC) was sent to prescribers (8th November 2022)(11) and Marketing Authorisation Holders (MAH) had one month to implement changes (28th December 2022). Dates for national-level interventions varied, especially in the case of France, where additional interventions were put in place between 2018 and 2021.

The overall aim of the study is to describe how prescribing of NOMAC and CMA has changed following the introduction of risk minimisation measures (RMM) in November 2022. To contextualise findings, it is also of interest to study changes in prescribing of other relevant drug classes, including progestogen and oestrogen combination products and progestogens that are pregnadien derivatives, and to study the impact of prior EU-level restrictions in trends of NOMAC prescribing.

D2 C	2 000	Charles	Donate and
P3-C.	3-UU6	Stuav	Protocol

Version: V4.0

**Dissemination level:** Public

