## Table 8. Operational definitions of outcomes.

Outcome name 	Details	Primary outcome?	Type of outcome	Washout window 	Care Settings 	Code Type⁴	Applied to study populations
Progestogen and estrogen combination products	For incidence/prevalence calculations (Objective 1).	Yes	Count	[-365, -1]	IP, OP	RxNorm	General population (objective 1 and 6)
Progestogens that are pregnadien derivates	For incidence/prevalence calculations (Objective 1).	Yes	Count	[-365, -1]	IP, OP	RxNorm	General population (objective 1 and 6)
Medroxyprogesterone	For incidence/prevalence calculations (Objective 1).	Yes	Count	[-365, -1]	IP, OP	RxNorm	General population (objective 1 and 6)
NOMAC	For incidence/prevalence calculations (Objective 1 and 6).	Yes	Count	[-365, -1]	IP, OP	RxNorm	General population (objective 1 and 6)
СМА	For incidence/prevalence calculations (Objective 1 and 6).	Yes	Count	[-365, -1]	IP, OP	RxNorm	General population (objective 1 and 6)
Progestogen and oestrogen combination products not containing NOMAC or CMA	To assess line of treatment and switches to alternative treatments (Objective 4 and 5).	Yes	Binary	N/A	IP, OP	RxNorm	New users of NOMAC or CMA (objective 2, 4 and 5)
Progestogens that are pregnadien derivates not containing NOMAC or CMA	To assess line of treatment and switches to alternative treatments (Objective 4 and 5).	Yes	Binary	N/A	IP, OP	RxNorm	New users of NOMAC or CMA (objective 2, 4 and 5)
Meningioma	Diagnosis of meningioma	Yes	Binary	[-Inf,-1]	IP, OP	SNOMED	New users of NOMAC or CMA (objective 2, 4 and 5)

<sup>1 NOMAC = nomegestrol, CMA = chlormadinone

<sup>2 For outcomes relative to objective 1 and 6, the washout window will be applied for incidence calculations only.

 $^{3}$  IP = inpatient, OP = outpatient, ED = emergency department, OT = other, n/a = not applicable.

<sup>4 RxNorm codes will be identified based on the vocabulary hierarchy, with ATC codes being ancestors.

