#### **Medications of interest:**

#### Drug classes of interest:

- Progestogen and oestrogen combination products not including NOMAC or CMA.
- Progestogens that are pregnadien derivates not including NOMAC or CMA.
- NOMAC (high- and low-dose products, assessed separately)
- CMA (high- and low-dose products, assessed separately)
- Medroxyprogesterone

Drugs used in the management of conditions for which medications of interest might be prescribed:

- Antidepressants
- Antihyperglycemics (Metformin)
- Bisphosphonates
- Clonidine
- Gonadotropin Releasing Hormone antagonists
- Anti-androgens (bicalutamide, flutamide, finasteride, spirolactone, cyproterone acetate)

A preliminary list of concepts to identify pre-specified comorbidities and comedications is detailed in the **Appendix I**. Comorbidities will be measured for any time prior to 1 day before index date, 365 days prior to 1 day before index date and at index date. Concomitant medications will be described 365 days prior to 31 days before index date, and 30 days to 1 day before index date, and at index date.

The operational definition of the covariates is described in the Table 9.

Authors: [name], [name], [name], [name], [name]

Version: V4.0

Dissemination level: Public

**Table 9.** Operational definitions of covariates.

Characteristic	Details	Type of variable	Assessment window	Care Setti ngs 	Code Type	Diagn osis Positi on 	Applied to study populations
Age groups	Defined as: 10-17, 18-34, 35-49, 50-64, +65.	Categorical	N/A	IP, OP	N/A	N/A	General population (objective 1 and 6)
Dose (NOMAC and CMA)	High vs. low doses. For NOMAC, high doses will include amounts from 3.75mg to 5mg. For CMA, high doses will include amounts from 5mg to 10mg. Low doses will be any amounts less than those specified.	Categorical	0	IP, OP	N/A	N/A	General population (objective 1 and 6)
Indication	Non-HRT vs. HRT. Age will be used as a proxy (non-HRT in women aged 10-49 years, HRT in women aged >50 years).	Categorical	0	IP, OP	N/A	N/A	General population (objective 1 and 6)
Comorbidities	Large-scale characterisation and pre-specified conditions 	Binary	[-Inf, -1], [- 365,-1], 0	IP, OP	SNO MED	Any	New users of drug classes or progestogens of interest (objective 3)

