## Objective 5:

[figure not shown]
We will describe the number and proportion of patients that follow different treatment strategies in the 180 days following the end of treatment. These strategies are defined as:

- Restart the same treatment
- Switch to a different treatment
- Restart and switch to a different treatment
   Discontinued treatment (not treated, neither with the original treatment nor any potential switch)

For this objective (time period comparison), both incident and prevalent users will be considered. The proportion of individuals following each treatment strategy (e.g. switching) will be calculated using the number of people exposed to the product of interest during the time period under study (e.g. pre-intervention) as the denominator regardless of when the initiation started.

Figure 2 illustrates some of these scenarios.

**Figure 2.** Outcomes after the drug exposure of interest (in blue) over different time periods.

Source: DrugUtilisation R package website (22)

The number of meningioma cases occurring any time during treatment with NOMAC or CMA, and in the six months prior to the end of treatment will also be reported. For cases identified in the six months prior, we will report the treatment strategy followed after treatment (i.e. restart, switch, both, or discontinuation).

NOMAC and CMA will be assessed separately. Results will be reported overall and stratified by study period (pre- vs. postintervention) and WHO 5th ATC level codes (if counts allow). For the pre- and post-intervention comparison, treatments initiated during the 180 days before the intervention will not be considered, to ensure sufficient time for assessing outcomes (e.g., switches, discontinuations) prior to the intervention.

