# **Pre-specified medications:**

Pre-specified medications	WHO ATC codes 
Antidepressants	N06A
Anti-androgens	L02BB, C03DA01, G04CB01, G03H
Biophosphonates	M05BA
Clonidine	C02AC01
Metformin	A10BA02
Gonadotropin Releasing Hormone antagonists	L02AE02
Selective Estrogen Receptor Modulators	G03XC

<sup>1 All descendants included.

Authors: [name], [name], [name], [name], [name]

Version: V4.0

Dissemination level: Public

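### Cyproterone acetate and medroxyprogesterone alone are not in the Objective 4/5 alternative groups, so a move only to them counts as discontinuation and prior use only of them as first-line

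*Protocol*

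**What the plan says.** **Role given to cyproterone.** Protocol section 6 states of long-term use: "progestogens other than NOMAC such as cyproterone acetate (6) and medroxyprogesterone acetate (7) has also been linked to an increased risk of meningioma". Section 8.6.3, under the label "Drugs used in the management of conditions for which medications of interest might be prescribed", has the entry "Anti-androgens (bicalutamide, flutamide, finasteride, spirolactone, cyproterone acetate". Appendix I codes the anti-androgens together as "L02BB, C03DA01, G04CB01, G03H". Section 8.6.3 and Table 9 use this list for Objective 3 only, in windows that end on or before the index date.

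**What counts as an alternative.** Table 8 has two outcome groups with the purpose "To assess line of treatment and switches to alternative treatments (Objective 4 and 5". They are the two drug classes with NOMAC and CMA removed. The abstract defines those classes as "Progestogen and oestrogen combination products (WHO ATC G03AA, G03AB, G03FA and G03FB") and "Progestogens that are pregnadien derivates (WHO ATC G03DB"). Appendix I repeats the same codes for Objectives 4 and 5.

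**How the alternatives are used.** Section 8.8, Objective 5, sorts women by what happens in the 180 days after treatment ends: restart, switch, both, or "Discontinued treatment (not treated, neither with the original treatment nor any potential switch"). Objective 4 looks back for records of the other drug classes of interest and labels the NOMAC or CMA treatment first or non-first. For Objectives 2 to 5, the proportions discontinuing and switching are each compared before and after the measures by their own standardised mean difference.

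**The concern.** The protocol itself names cyproterone as a progestogen linked to the same tumour and lists it for overlapping conditions, but gives it no place after NOMAC or CMA ends and none as an earlier line. Medroxyprogesterone, named in the same sentence of the rationale, has its own Objective 1 series; cyproterone has none, and no reason is given.

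What is at stake is the split between two separately reported results. A reader of the Objective 5 table would take the discontinued row to mean women left without a comparable hormone, when some may have moved to another progestogen that the rationale flags. In Objective 4, first-line use of NOMAC or CMA, which the 2022 measures address for high-dose products, would include women who had already tried cyproterone. Section 11 discusses indication, code mapping and look-back for these analyses but does not mention this exclusion.

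**Working it through.** No figure in the protocol bears on this, so the check compares code sets and traces individual women through the definitions.

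**1. Code sets (Appendix I)**
- Alternatives for Objectives 4 and 5: G03AA, G03AB, G03FA, G03FB and G03DB, less the NOMAC and CMA codes.
- Anti-androgens, including cyproterone: L02BB, C03DA01, G04CB01, G03H.
- Codes in common: none. The protocol does not say which of the four codes holds cyproterone, but none of them is a switch code.

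**2. Objective 5.** A woman ends NOMAC or CMA and in the next 180 days receives only cyproterone. She has no restart and no listed switch, so she falls into the residual category, discontinued. If she also receives a listed class she is counted as switched. If she restarts, she is counted under restart and does not enter the discontinued row.

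**3. Objective 4.** A woman whose only earlier drug was cyproterone has no qualifying record in the look-back. Her NOMAC or CMA treatment is counted as first.

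**4. Size.** Section 8.8 takes as denominator everyone exposed to the product in the period. As shares of that denominator, let s be the women who move only to cyproterone, W those with a listed switch, and D those with no restart, no listed switch and no cyproterone.

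| | Switched | Discontinued | Sum |
|---|---|---|---|
| As written | W | D + s | W + D + s |
| Cyproterone counted as a switch | W + s | D | W + D + s |

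Each row is off by s and the sum is the same. The error in the pre/post difference is s(post) − s(pre), which is zero if the shares are equal. The documents give no value for s. For an assumed range of 0 to 10%, each proportion is off by 0 to 10 percentage points. If only a fraction e of exposed women end treatment and a share r of those move only to cyproterone, then s = e × r, which cannot exceed r.

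**5. Medroxyprogesterone (Appendix I codes)**
- G03AA08 and G03AA17 lie in G03AA, G03FA12 in G03FA and G03FB06 in G03FB: inside the alternatives.
- G03AC06 and G03DA02: outside.
- L02AB02: outside, and marked for exclusion as oncological where possible.

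A move only to G03AC06 or G03DA02 is therefore also counted as discontinuation. Section 7, however, lists medroxyprogesterone-containing products among the relevant classes and says relevant classes will be considered for line of treatment and switches.

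**The case against.** **This is a scope choice.** The protocol limits switching and line of treatment to its drug classes of interest throughout, and the discontinued category is defined relative to those switches. That stands for cyproterone: the text does not contradict itself, and the category does not claim that the woman receives no treatment of any kind. It does not remove the case for reporting or disclosing the exclusion, given what the rationale says.

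**Substitution is not shown.** The section 8.6.3 list also holds antidepressants, metformin, bisphosphonates and clonidine, so it is a characterisation list and does not name substitutes. Nothing in the protocol shows how often women move from NOMAC or CMA to cyproterone. That stands, and it is why no size can be given.

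**Objective 3 already reports anti-androgens.** It does so only up to the index date. Its population in Table 4 is first-ever users of any drug class of interest, which is not the Objective 4/5 cohort.

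**A stronger inference to avoid.** A reader might infer that a rise in discontinuation after the measures would be an artefact, or that the design favours the expected result. The documents support neither. A woman moved to cyproterone has stopped NOMAC or CMA. The Objective 5 hypothesis in Tables 1 and 11 expects both switches and discontinuations to rise, so moving her between the two rows does not manufacture support for it. A spurious change over time would also need the share moving to cyproterone to differ between periods, and the protocol gives no evidence on that.

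**Conclusion.** The point holds as a gap in the outcome definitions that the limitations do not disclose. By the protocol's own code lists, a move only to cyproterone, or only to medroxyprogesterone under G03AC06 or G03DA02, is reported as discontinuation, and prior use of only these drugs is reported as first-line treatment.

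The effect is confined to women with no restart and no listed class. It shifts the separately compared switch and discontinuation proportions by equal and opposite amounts. Its size is unknown, and the 0 to 10 point range is an assumption. The pre/post comparison is affected only if the shares differ between periods.

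Two assumptions remain. Cyproterone is taken to sit under one of the four pooled anti-androgen codes, as sections 8.6.3 and Appendix I together imply. The ATC-to-RxNorm mapping is taken to work as intended; section 11 admits inconsistencies for combination drugs, so some cyproterone combinations could be caught by accident.

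The medroxyprogesterone gap is the better documented of the two, because it is a declared progestogen of interest. The change is worth making before the code is run.

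**What to change.** In Table 8 and Appendix I, add two groups for Objectives 4 and 5:
- cyproterone-containing products, using the cyproterone codes within the existing anti-androgen list once these are confirmed;
- non-oncological medroxyprogesterone, including G03AC06 and G03DA02.

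Report each as its own switch destination in Objective 5 and its own prior treatment in Objective 4. Keep the current definition as a parallel output, so that results under the stated scope remain available. Reconcile section 7 with Table 8 on whether medroxyprogesterone alone counts. A descriptive monthly cyproterone series in Objective 1 is optional. If the scope is kept as it is, say in section 11 that moves to these drugs are counted as discontinuation and prior use of them is ignored.

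The cost is a few more output rows from the same data, with a starting code list already in Appendix I. Table 3 gives feasibility counts for NOMAC and CMA only, so some new cells may be suppressed as <5.
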